In a survey of 80 obstetrical nurses from 3 large hospitals in Florida, over 30% stated that a major barrier to assisting mothers of VLBW infants to begin timely breast milk expression following delivery was a lack of time and lack of personnel.

Primary purpose of this pilot study is to determine the feasibility and potential effect of a prenatally delivered lactation education program for expectant mothers of premature infants and their support person (SP) on timing of initiation of milk expression, lactation success, and stress

Specific aims are as follows:

Aim 1: To evaluate the feasibility of antenatal BM pumping education for SPs of mothers of preterm infants. Issues related to recruitment, randomization acceptance of the intervention, and refinement of the education materials and process will be scrutinized. Aim 2: To estimate variability of outcome measurements and effect sizes needed to calculate the sample size for a subsequent larger, adequately powered, randomized clinical trial

Research Plan:

Research Design

A randomized clinical trial will be conducted to determine the effect of a prenatally delivered lactation educational program for expectant mothers of premature infants and their SP on timing of initiation of milk expression and lactation success. Timing of lactogenesis stage II will be documented, volume of breast milk produced will be measured for the first 3 weeks following delivery and duration of lactation will be documented. Stress regarding the initial milk expression session will be measured. Breast milk sodium levels will be measured at Day 1-7, Day 14 and 21

Sample and Setting

80 mothers who have been hospitalized anticipating the delivery of a premature infant will be sampled by convenience from a maternity unit at Shands Teaching Hospital, a Level III tertiary care center. The hospital is part of the University of Florida and includes a Level III (52 bed) NICU. The hospital catchment area encompasses North Central Florida and Southern Georgia, a predominantly rural and semi-rural population. 120 VLBW infants per year are delivered with 95% of these women electing to express breast milk for their infants. This will also include enrollment of 80 support persons as a couplet with mom.

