Inclusion criteria for the mothers are: 1) at least 18 years of age, 2) English speaking, 3) stated intent to breastfeed, 4) anticipating the birth of a premature infant < 35 weeks gestation. Exclusion criteria are: 1) known illicit maternal drug use, 2) history of breast reduction or augmentation, 3) positive HIV status, or 4) infant not expected to live over 2 weeks following delivery.

Inclusion criteria for the support person: 1) is expected to be present immediately following delivery, 2) at least 18 years of age, 3) English speaking

Randomization

Informed consent will be obtained from both mother and SP prior to delivery. Following consent, the pair will be randomly assigned to one of two groups. Group 1 will receive a prenatally delivered lactation educational program. Group II will receive standard care.

Procedure

Once the pair is randomly assigned to one of the groups, the PI, or a research assistant will make an appointment and meet with the mother and her support person (the person or persons stated to be with her during labor and the delivery of her infant). During this meeting the mother and her support person will be provided the following educational activities

1. Viewing of a video regarding the benefits of breast milk for premature infants.
2. Viewing of video with instructions regarding how to use a breast pump and instructions regarding milk expression.
3. They will be given the standard written and verbal pumping instructions provided to all mothers who are pumping breast milk for their infants.

4. A hospital grade breast pump and all necessary equipment for milk expression will be provided and will remain in the mother's hospital room. A demonstration of how the pump works and how to set up the pump will be provided.

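### Pairs are randomised before the education is booked, with no limit on the interval, so some Group 1 pairs may deliver before they are taught

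*Combined protocol and SAP*

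**What the plan says.** All references are to the combined protocol and SAP.

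- **Population (Sample and Setting).** The sample is "80 mothers who have been hospitalized anticipating the delivery of a premature infant will be sampled by convenience". The eligibility criterion on timing is "anticipating the birth of a premature infant < 35 weeks gestation". No minimum expected time to delivery is required.
- **Consent and allocation (Randomization).** "Informed consent will be obtained from both mother and SP prior to delivery", and then "Following consent, the pair will be randomly assigned to one of two groups".
- **Intervention (Randomization).** "Group 1 will receive a prenatally delivered lactation educational program"; the other group has standard care.
- **Teaching (Procedure).** This is arranged only after allocation: "Once the pair is randomly assigned to one of the groups, the PI, or a research assistant will make an appointment". Both members of the pair are to attend. The videos, the pumping instructions, the pump demonstration and the in-room pump all come at this meeting. Read literally, the sentence covers pairs in either group, but the Abstract and the Randomization section confine the program to Group 1.

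The protocol gives no maximum time from randomisation to the meeting and no rule for a Group 1 pair whose baby is born first. Table 2 has no item for whether or when the education was given (the appendices are not shown). There is no statistical analysis section, so the analysis set is not stated.

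**The concern.** The program has to precede birth, yet allocation is fixed before the teaching is arranged, in women who may deliver at short notice. The meeting also depends on the support person being there. A Group 1 pair can therefore be randomised and then be unable to receive the intervention.

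Two things are at stake. Aim 2 uses the pilot's effect sizes to plan a larger trial. If untaught pairs stay in Group 1, the estimated effect is diluted. If they are dropped from Group 1 only, that group loses its fastest deliveries while the control group keeps its own, and the groups are no longer balanced on urgency of delivery. The Insufficient Milk Supply section says that milk volume is correlated with gestational age, so the imbalance could reach a main outcome if the urgent deliveries are also the earlier ones.

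For Aim 1, failure to teach before birth is a feasibility finding in its own right, but the plan does not provide for counting it.

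**Working it through.** **The plan's own figure.** The 80 mothers cannot be re-derived, because no effect size, SD, alpha or power is given.

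**Inputs.** From the documents: 80 pairs in two groups. Assumed, because not stated:

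- equal allocation, so 40 pairs per group;
- a share *p* of Group 1 delivering before the meeting, from 5% to 30%;
- untaught Group 1 pairs do no better than controls;
- every pair is analysed as randomised, with the SD unchanged;
- for illustration only, a standardised effect *d* = 0.5 in taught pairs, two-sided alpha 0.05 and 80% power.

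**Formulas.** All-randomised effect = (1 − p) × effect in taught pairs. Required sample size varies as 1/effect², so its ratio is 1/(1 − p)². For example, at p = 0.20 the effect is 0.80 of the taught effect, and the ratio is 1/0.64 = 1.56.

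| p | Untaught of 40 | Effect retained | Sample-size ratio | d (from 0.5) | Next trial, n per arm |
|---|---|---|---|---|---|
| 0 | 0 | 100% | 1.00 | 0.500 | 63 |
| 5% | 2 | 95% | 1.11 | 0.475 | 70 |
| 10% | 4 | 90% | 1.23 | 0.450 | 78 |
| 20% | 8 | 80% | 1.56 | 0.400 | 99 |
| 30% | 12 | 70% | 2.04 | 0.350 | 129 |

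Mixing taught and untaught pairs also widens the SD slightly: at p = 30% and d = 0.5, √(1 + 0.5 × 0.3 × 0.7 × 0.25) = 1.013. This is ignored above.

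**Could it happen at all?** The chance that at least one of 40 pairs is untaught is 1 − (1 − p)^40. That is 33% at an individual risk of 1%, 55% at 2%, 87% at 5% and 98.5% at 10%.

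**Scale against the pilot's precision.** With 40 per group, the 95% half-width for d is about 1.96 × √(2/40) = 0.44. At d = 0.5, the shift is 0.05 at p = 10% and 0.10 at p = 20%.

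**The case against.** The strongest reply is that the plan describes a sequence, not a delay. For an inpatient the meeting could take place the same day, and the appointment has an evident purpose, which is to bring mother and support person together. A reader might infer that some Group 1 mothers are certain to deliver untaught. The documents do not support that, since they give neither an interval nor an early-delivery rate. This part of the reply stands, and the point is about what may happen.

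Three further replies stand in part.

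- **Planning value.** If the next trial teaches in the same way, the all-randomised effect, untaught pairs included, is the correct figure to plan with. It misleads only if it is read as the effect of education received, or if the next trial delivers the program differently. Even under the same procedure, though, the larger sample is a cost that reordering could avoid.
- **Zero benefit.** The Procedure section gives mothers a visit before discharge with further instruction if needed, access to lactation services, and a hospital-grade pump during their stay. Untaught pairs may gain something on milk volume or lactogenesis II. No benefit is more plausible for time to first expression.
- **Aim 1.** The aim already covers recruitment, acceptance and process, and a survey asks about the educational experience. Whether the teaching can be done before birth is a proper question for a pilot. But no count of it is specified.

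**Conclusion.** The point holds in conditional form. The order of steps, the inpatient population and the absence of any limit on the interval are all in the text. How often a pair would go untaught is not. For 5% to 30% untaught, the estimate would be 95% to 70% of the effect in taught pairs, and the implied sample size 1.11 to 2.04 times as large. This rests on equal allocation, no benefit to untaught pairs, and analysis as randomised.

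The shift is systematic and in one direction. At d = 0.5 and 10% to 20% untaught it is nevertheless 0.05 to 0.10, against a half-width of about 0.44, so it does not undermine the pilot. Two stronger readings should be resisted. One is that Aim 2's estimate is wrong: it is not, if the next trial keeps this procedure. The other is that the plan excludes untaught pairs: it does not say so, and selection bias would arise only if they were dropped from Group 1. What remains is an avoidable loss that is cheap to remove.

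**What to change.** 1. Open the allocation at the contact where mother and support person are both present and the second of them consents, and teach Group 1 at that contact. Where this is not possible, randomise at the start of the first joint meeting. Pairs lost to early delivery are then lost before allocation, where they cannot bias the comparison.
2. Record the date and time of consent, randomisation, education and birth for each pair.
3. Report two Aim 1 feasibility results: the number of consented pairs who deliver before allocation, and the proportion of Group 1 taught before birth.
4. State that every randomised pair is analysed in its assigned group.

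**Cost.** No new staff or procedure is needed, but the video and pump must be to hand when consent is taken. Some consented pairs will not be randomised, so the randomised sample is limited to pairs reached before delivery. The fallback costs more: if the wait for a joint meeting were unchanged and 10% to 30% of 80 consented pairs delivered first, 8 to 24 would be lost before randomisation. That is why allocation and teaching at the consent contact should be the main rule.

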Project Title

Prenatal breast pumping education of mothers and their support person

NCT # 04006509

Date
6/16/2019

RESEARCH PROTOCOL

Project Title:

Prenatal breast pumping education of mothers and their support person

Abstract:

Compelling evidence exists that breast milk helps protect premature infants from prematurity-specific morbidities, including feeding intolerance, late onset sepsis, and necrotizing enterocolitis. Unfortunately, mothers of VLBW infants often exhibit delayed lactogenesis stage II (when the milk "comes in") and inadequate breast milk production. Earlier initiation of breast milk expression following delivery is associated with increased lactation success. However, lack of nursing time and lack of hospital personal are significant barriers to the early initiation of milk expression in this population. The proposed study will follow a prospective cohort of racially and economically diverse mothers of premature infants for 3 weeks following delivery to test 1 *primary aim* and 1 *secondary aim*. **Aim 1:** will evaluate the feasibility of antenatal BM pumping education for SPs of mothers of preterm infants. Issues related to recruitment, randomization acceptance of the intervention, and refinement of the education materials and process will be scrutinized. **Aim 2** will estimate variability of outcome measurements and effect sizes needed to calculate the sample size for a subsequent larger, adequately powered, randomized clinical trial. Eligible women and their SP will be randomly assigned to one of two groups. Group 1 will receive a prenatally delivered lactation educational program including video recordings, a demonstration of how the pump works and will have a breast pump available in their room. The volume of breast milk produced, timing of lactation stage II, duration of lactation and stress during initial expression will be measured. In addition, breast milk sodium levels will be analyzed on Day 1-7, Day 14 and 21.

Background:

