Healthy People 2020 goals include an exclusive breastfeeding rate of 46.2% for the first 3 months of life (Healthy People, 2020). This is rarely attained in term infants and due to an insufficient milk supply, even less likely to occur in mothers of VLBW infants thus depriving them of the essential benefits of breast milk. Milk volume in these mothers also often substantially decreases at around 3 to 4 weeks following delivery resulting in a further decrease in the number of women providing breast milk to their infants (Hill et al., 2005a)

Preliminary Work

In order to improve breastfeeding success, it is strongly recommended that women who deliver term infants begin breastfeeding within 30-60 minutes following delivery. In our pilot work we mimicked normal term parturition, by initiating milk expression in mothers of VLBW infants with a gestational age between 23 and 32 weeks ($n=20$) within 1 hour following delivery ($n=10$) and compared milk volume and timing of lactogenesis stage II with mothers who began milk expression 1-6 hours following delivery ($n=10$). *Only 1 mother who was approached declined to participate in the study. No statistically significant differences were found between the groups for demographic characteristics or behavioral factors including kangaroo care and expression frequency.* Although the study was small ($n=20$), women who began milk expression within 1 hour following delivery produced statistically significant more milk during the first 7 days. *Total milk volume expressed by women who expressed within 1 hour following delivery was over twice that of mothers who began milk expression later. Women who began milk expression in the first hour also produced significantly more milk at 3 weeks following delivery and also had a statistically significant earlier lactogenesis stage II. Stress and pain associated with initial milk expression session was also analyzed between groups with no significant differences found between groups. Women in the earlier expression group tended to report less stress and pain (Parker et al., 2012).*

In addition, we compared women who began milk expression within 6 hours versus those who began milk expression after 6 hours following delivery and found those who began milk expression within 6 hours produced more breast milk in the first 7 days following delivery

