Mothers will be visited by the research coordinator, PI, or a research assistant prior to her discharge from the hospital ensure they are successfully using the breast pump and to provide additional instruction if needed. Mothers will also have access to lactation services and nurses on the unit. At this visit, mothers and the SP will be questioned regarding stress associated with the initial milk expression (Appendix A). Participants will be asked to indicate their level of stress on a visual analogue scale and will mark their response on a 100mm horizontal line continuum from none to severe. The score was determined by measuring in millimeters from the left hand end of the line to the point where the subject marked. Since single-item measurements are easier to administer, less burdensome to participants and have been shown to be a valid and reliable tool, participants will be asked to answer only one question pertaining to stress. The mother and SP will also be asked to complete a survey regarding the educational experience (Appendix B,C).

Mothers will be provided with a supply of pre-weighed milk vials and labels in which they will place the milk following expression per standard NICU policy. During hospitalization or while visiting their infant in the NICU, mothers will have a hospital grade electric pump available for use. Upon discharge, all mothers will be provided the same hospital grade electric pump for use while their infant is in the NICU and they continue to lactate. Mothers will be asked to bring vials from all pumping sessions to the NICU, regardless of apparent results. While mothers are still hospitalized, the mother or nurse will bring the vials to the NICU following each expression, where they will be deposited in a refrigerator specified for storage of breast milk for all infants in the NICU. Once mothers go home, they will be instructed to store their vials of expressed breast milk in the refrigerator or freezer at home, and to bring vials to the NICU when visiting their infants (standard NICU policy). All breast milk will be weighed by a breast milk technician blinded to the group assignment (Appendix D). Mothers will be reminded 3 times per week—through phone calls, texts or during visits to the NICU—to bring in their breast milk when they visit.

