Measurement of milk volumes by weight will occur at the initial expression session, for the first 7 days, and on day 14 and 21. (see Table 2 for a list of all instruments). If the infant breastfeeds during the 24-hour period, test weighing will be used to calculate breast milk consumed. *Test weighing* or the weighing of infants prior to and following breastfeeding, has been shown to be an accurate method of determining intake during breastfeeding in preterm infants. Prior to each breastfeeding session, infants will be weighed by the nurse assigned for patient care, and weight will include the clothing, diaper and/or blankets infant is wearing. Following completion of the breastfeeding session, the infant will be weighed again, clad in the same clothing as with initial weight. Infants will be weighed on the Baby Weigh scale (Medela, Inc, McHenry, III) to the nearest 0.2 g. The Baby Weigh scale is a portable electronic digital scale that is accurate to within 0.2 grams. The scale will be calibrated by the study coordinator prior to initiation of the study and after every 10 measurements, using 0.2mg, 1 mg, 10mg and 50 mg weights. All weights will meet or exceed ASTM (American National Standards Institute) specifications and will be calibrated by a NVLAP (National Institute of Standards and Technology) accredited lab. The difference between the pre and post-feeding weights will be recorded on the Breastfeeding Data Collection Form taped at the infant's bedside and will be added to the total amount the mother expressed during that 24-hour period (Appendix E).

A < 0.5 mL of breast milk will be obtained daily (if the mother is expressing > 5mL of breast milk per day) daily during days 1-7, day 14, day 21 and the sodium level analyzed

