Maternal mood can impact breastfeeding success in term infants and it is possible it may also impact BM production and timing of lactogenesis stage II in mothers of VLBW infants. Prior to her discharge from the hospital and 7 days following delivery, mothers will be asked to complete the MAACL-R; a standardized instrument with well-documented psychometric properties that assesses mood states by using positive and negative mood state scales for Anxiety, Depression, Hostility, Positive Affect and Sensation Seeking. It consists of 132 adjectives at or below an 8th grade reading level, takes approximately 3 minutes to complete. This test has been successfully used in lactating mothers of premature infants and was used in our previous

research. The second test will be completed around day 7 and will be provided to mothers prior to discharge. Mothers will be phoned by the research coordinator on to remind them to complete the test. Mothers will return the test when they visit their infant and results will be manually scored by the research coordinator.

Table 2. Instruments (Logs)

| Variable | Instrument | Measurement |
|---|---------------------------------------|--|
| Demographics (Appendix F, G) | Log maintained by Research Assistant | Age, parity, diabetes, pregnancy induced hypertension, mode of delivery, type of anesthesia, experience with breastfeeding, smoking, obesity, antenatal steroids |
| Lactation Factors (1-3 below) | | |
| 1. Onset of lactogenesis stage II | Log maintained by Research Assistant | Date and time of sensation of breast fullness Corresponding breast milk measurement |
| 2. Sodium level in breast milk | Log maintained by Research Assistant | Date/Sodium level in breast milk corresponding to onset of lactogenesis II |
| 2. Milk volume | Log maintained by Research Assistant | Daily total breast milk weight for days 1-7 24 hour sample at Day 14,21 |
| 3. Milk volume alternative for breastfed infants | Log maintained by Research Assistant | (Test weighing) - difference in infant's weight before and after feeding as indicator of breast milk intake. |
| Kangaroo care | Log maintained by RA | Incidence and length of kangaroo care in minutes extracted from medical record |
| Infant breast milk intake | | |
| 1. Weekly percentage of breast milk received by infant during first 3 weeks of life | Log maintained by Project Coordinator | Data extracted from medical record |

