All subjects eligible for enrollment will be registered and entered into the study database designed by the program assistant. The system includes designated web servers and supporting database servers. Study data will be directly entered into the database via a secure internet connection. The system allows the PI to access data in real-time and to generate reports based on enrollment status, basic demographics, and data summaries. The web-based data system will also allow for the sharing of data in the future. The system will assign a global unique identifier to each enrolled subject that will serve as the unique subject id. Personal Health Information will not be stored in the study database. The study case report forms (CRFs) will be maintained in study specific folders. The CRFs are considered the primary data collection instruments for this study. When CRFs are not actively being processed, they will be secured in locked file cabinets. In addition to the use of passwords and other security measures, all documents containing identifying information are considered confidential materials and are safeguarded to the greatest possible extent. No individually identifying information will be released or discussed with anyone other than study staff.

Possible Discomforts and Risks:

Possible risks include stress regarding the education process and for the support person, it may be stressful to assist the mother in breast milk expression. This will be measured

Possible Benefits:

Mother who with their support person receive antenatal education may have an earlier initiation of milk expression and have increased lactation success.

Conflict of Interest:

There are no conflicts of interest

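### Does taking milk sodium only on days above 5 mL bias the sodium estimates that Aim 2 could carry forward?

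*Combined protocol and SAP*

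**What the plan says.** Under Procedure, a milk aliquot of under 0.5 mL "will be obtained daily (if the mother is expressing > 5mL of breast milk per day"), on days 1-7, 14 and 21, for sodium analysis. Two other places give the same schedule without the volume condition. The Abstract says "breast milk sodium levels will be analyzed on Day 1-7, Day 14 and 21" and Research Design says "Breast milk sodium levels will be measured at Day 1-7, Day 14 and 21".

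Aim 2, under Specific aims, is "To estimate variability of outcome measurements and effect sizes needed to calculate the sample size" of a later trial. It does not list the outcomes.

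Table 2 defines one sodium entry: "Date/Sodium level in breast milk corresponding to onset of lactogenesis II". The text after Table 2 says that mothers' reports of onset will be checked against more than 100 mL per 24 hours.

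On volume, Procedure asks mothers to "bring vials from all pumping sessions to the NICU, regardless of apparent results", and all milk is weighed. Possible Benefits states that educated pairs "may have an earlier initiation of milk expression and have increased lactation success". The document has no analysis section for any outcome.

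**The concern.** Consent and randomisation come before delivery (Randomization), so the volume expressed on a given day is a post-randomisation variable. It is also an outcome that the programme is meant to improve. Under Preliminary Work, an earlier comparison by time of first expression (n=20) reports: "Total milk volume expressed by women who expressed within 1 hour following delivery was over twice that of mothers" who began later. That was a timing contrast, not this programme, but it makes a volume effect plausible.

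If volume rises in Group 1, more of its low producers pass 5 mL and are sampled. On that day the sampled mothers in the two groups are no longer comparable, and randomisation does not protect the sodium contrast. The sampled SD also describes a restricted group, even when volumes are equal. Either quantity, carried into the next trial's sample size under Aim 2 without its condition, could mislead. Low early volumes are likely here: the background reports delayed or impaired lactogenesis II in up to 82% of women who deliver prematurely.

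**Working it through.** The plan states no sodium figure, so there is nothing to reproduce. The check asks how large the effect could be, and on which quantity it would fall.

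**Inputs.** From the document: the 5 mL threshold, 80 mothers, two groups. Assumed: 40 per arm; log-normal daily volume with log SD 1; intervention-to-control volume ratio 1.2 to 2; within-arm correlation rho of sodium with log volume of -0.4 to -0.8; control median 5, 10, 20 or 50 mL.

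**Formulas, per arm.** a = ln(5/median); proportion sampled p = 1 - Phi(a); lambda = phi(a)/p; delta = lambda(lambda - a). In units of the unselected sodium SD:
- shift in the sodium difference (intervention minus control) = rho(lambda1 - lambda0)
- sampled variance v = 1 - rho^2 delta
- SE = sqrt(v0/(40 p0) + v1/(40 p1))

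**Extreme case: control median 5 mL, ratio 2, rho = -0.8.**
- Control: a = 0, p = 0.50, lambda = 0.798, SD = 0.770.
- Intervention: a = -0.693, p = 0.756, lambda = 0.415, SD = 0.840.
- Shift = -0.8 x (0.415 - 0.798) = +0.306 SD. SE = 0.230. The shift is 1.33 SE.

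**Range by control median.**

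| Control median | Shift (SD) | Shift in SE |
|---|---|---|
| 5 mL | +0.045 to +0.31 | 0.15 to 1.3 |
| 10 mL | +0.03 to +0.20 | 0.1 to 0.9 |
| 20 mL | +0.02 to +0.10 | 0.1 to 0.4 |
| 50 mL | at most +0.02 | at most 0.1 |

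With rho = +0.4 the 5 mL shift is -0.045 to -0.15 SD. With rho = 0, or equal volumes in the two arms, it is 0. The sign therefore rests on an assumption.

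**Consequence for the next trial's size.** This depends on the scenario.
- *Volumes equal, sodium difference fixed, next trial samples every mother.* At 5 mL the sampled SD is 0.948 to 0.770. Its square is 0.90 to 0.59, so the next trial would be 10% to 41% too small.
- *Programme acts on sodium only through volume.* The unselected difference is rho x ln(ratio). In the extreme case this is -0.8 x 0.693 = -0.555 SD, and sampled mothers show -0.555 + 0.306 = -0.248 SD. The mean sampled variance is (0.770^2 + 0.840^2)/2 = 0.65. The required size is multiplied by 0.65 x (0.555/0.248)^2, about 3.2. Across the four corners of the assumed range at 5 mL the factor is 3.2 to 6.1, so the next trial would be too large.
- *Next trial keeps the same sampling rule.* The conditional SD is then the right planning input.

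**The variable the plan does define.** Sodium at onset of lactogenesis II is tied to a day checked against more than 100 mL, and 100/5 = 20 times the threshold. The rule excludes almost nothing there.

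**Would a completeness rule help?** One could take sodium forward only from days with at least 95% sampled in each arm (38 of 40). With one arm at that cut-off and the other fully sampled, lambda = 0.109, so the shift is at most 0.8 x 0.109 = 0.087 SD and the SD is at least 0.937. But after discharge, milk is stored at home and brought in at visits, so samples will also be absent for unrelated reasons. If 5% are absent that way (assumed), the chance that one arm has at most 2 of 40 absent is 0.677, and for both arms 0.677^2 = 0.46. At 10% absent it is 0.223^2 = 0.05. A rule that counts every absent sample would often discard later days, on which the selection is slight.

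**The case for a change.** The strongest case for a change is that the mechanism is certain even though its size is not. The condition stands in the text, volume is both post-randomisation and an outcome, and Aim 2 excludes no measurement. Sodium is scheduled on nine days, seven of them in the first week, when volumes are lowest. No text says how days at or below 5 mL are reported. The remedy is also cheap: a reason code in the sodium log, a table of numbers sampled by arm and day, and a label on early-day results.

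Most of this stands as a description. An early-day sodium difference among sampled mothers is not a randomised comparison, and its SD is conditional on volume above 5 mL. What does not stand is the step to a defect in the plan. The estimate at risk is one that the document never says it will compute. The absence of a rule for unsampled days is not particular to sodium, since no outcome has an analysis section. Even those who press the point would keep the sampling rule, so no measurement and no stated result would alter. The classification they want can already be made, because volumes from all sessions are weighed.

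**Conclusion.** No change to the plan is needed. The selection on early days is genuine, but it concerns a hypothetical use of a supplementary measure in a feasibility pilot, and a competent analyst would fill the gap when reporting: sodium by day, with numbers sampled in each arm, early values described as conditional on more than 5 mL, and days with no milk kept apart from days above 0 and up to 5 mL. A day without milk cannot yield a sodium value under any rule.

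On size, the assumed model gives a shift of 0.045 to 0.31 SD at a 5 mL control median with negative correlation, fading to 0.02 SD or less at 50 mL. The top value needs a 5 mL median, doubled volume and a correlation of -0.8 together. The next trial could come out 10% to 41% too small or 3.2 to 6.1 times too large, depending on whether volume differs by arm and how the programme acts on sodium. The document supplies none of these inputs, so neither direction nor size can be asserted. The sodium value at onset of lactogenesis II is probably little affected. The missing volume condition in the Abstract and Research Design is abbreviation, since Procedure states the operative rule.
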